5.6.2.2. Progression-Free Survival (PFS)

PFS was originally defined as death due to progression in the protocol. However, to be consistent with regulatory guidance, which considers death from any cause in its definition, this endpoint was modified to be time elapsed between randomization and disease progression or death from any cause. Patients not known to have any of these events will be censored on the date they were last known to be event-free.

Progressive disease (PD) will be defined according to the section “AML-DISEASE EVALUATION” in the e-CRF as any of the following

- At least a 25% increase of BMBC compared with baseline (defined in the section “AML history / BM evaluation at baseline”, Bone Marrow Aspirate - Analyte - Blast)
- At least a 50% increase of PBBC compared with baseline
- Presence of extramedullary disease

Potential PD events presented by the patients will be reviewed and approved before database lock.

The methods for the analysis of PFS will be the same as those for OS. Specifically, PFS will be analyzed at the time of final analysis using a stratified log-rank test (stratified by PS) and displayed using Kaplan-Meier curves. Furthermore, a Cox model will also be used to test the effect of treatment and will include terms for prognostic factors (PS, age and karyotypic group).

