Resistant disease (RD)	BM blasts increase of at least 5% vs nadir AND/OR PBBC increase of at least 15% in absolute count vs nadir OR at least 50% in percentage vs nadir – repeated at min 7 days interval
Relapse¶	Bone marrow blasts \geq 5%; or reappearance of blasts in the blood; or development of extramedullary disease
Stable disease	Failure to achieve at least Partial Remission AND no Resistant Disease criteria

Table 3: Response criteria in AML

* All criteria need to be fulfilled; marrow evaluation should be based on a count of 200 nucleated cells in an aspirate with spicules; if ambiguous, consider repeat exam after 5 to 7 days; flow cytometric evaluation may help to distinguish between persistent leukemia and regenerating normal marrow; a marrow biopsy should be performed in cases of dry tap, or if no spicules are obtained; no minimum duration of response required. ¶ In cases with low blast percentages (5-10%), a repeat marrow should be performed to confirm relapse. Appearance of new dysplastic changes should be closely monitored for emerging relapse. In a patient who has been recently treated, dysplasia or a transient increase in blasts may reflect a chemotherapy effect and recovery of hematopoiesis. Cytogenetics should be tested to distinguish true relapse from therapy-related MDS/AML. (adapted Döhner *et al* 2010, Diagnosis and management of acute myeloid leukemia in adults: recommendations from an international expert panel, on behalf of the European LeukemiaNet, Blood, 21 Jan 2010, vol 15, no 3; 453 - 474)

5. Benefit – risk analysis

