15.3.3 Secondary endpoint analysis

Efficacy endpoints

All efficacy secondary endpoints will be analyzed in the ITT and PP populations.

Progression-free survival (PFS) will be analyzed as a secondary criterion of efficacy. PFS will be defined as the time from date of randomization and resistant disease or relapse or death from any cause. Any patient not known to have died at the time of analysis will be censored based on the last recorded date on which the patient was known to be alive (i.e. their status must be known at the censored date and should not be lost to follow up or unknown). PFS will be analyzed at the time of final analysis using a stratified log-rank test (stratification factor, PS). A Cox model will also be used to test the effect of treatment and will include terms for prognostic factors (PS, age and cytogenetic group).

The analysis of objective response rate (i.e. CR or PR) will be performed using logistic regression including treatment factor and PS. Secondary analysis will be performed where the logistic regression model will allow for the effect of treatment, and will also include prognostic factors as for OS and PFS. Percentage of patients with CR, CRi, CRp and PR will be calculated and associated exact 95% CIs will be presented by treatment group. Median duration of response from onset of response (RFS) will be calculated and summarized by treatment group for the subset of responders.

Absolute and relative change from baseline EORTC quality of life (QoL) questionnaire scores will be described in each treatment group. EORTC QoL questionnaire scores will be compared across time in each treatment group using a mixed model for repeated data.

Time until QoL deterioration will be defined as a decrease in QoL score from baseline without any return to a better state during the study. A threshold of 10% decrease in QoL score will be primarily used. Other thresholds may be used as exploratory analyses. Death will also be considered as a QoL deterioration. Time to QoL deterioration will be summarized using Kaplan-Meier methods and will be compared between treatment groups using a stratified log-rank test (stratification factor, PS).

Percentage of patients who need transfusions (red blood cells and/or platelets), mean number of transfusions by patient and mean number of hospitalizations (more than over 24 hours) required during the study will be described with their corresponding 95% CI in each treatment group.

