3.5. Efficacy, Pharmacokinetic, and Safety Variables

3.5.1. Efficacy Variables

The primary objective of this study is to evaluate the efficacy and tolerability of GRASPA when combined with LDAC. The primary endpoint is overall survival (OS), defined as the time elapsed between randomization and death for any cause. Patients not known to have this event are censored on the date they were last examined.

Secondary efficacy endpoints include the following:

- 1) Complete remission (CR), Complete remission with incomplete recovery (neutrophil or platelet regeneration, CRI), Partial remission (PR)
- 2) Progression-free survival (PFS) defined as the time elapsed between randomization and resistant disease or relapse or death from any cause
- 3) Relapse Free Survival defined only for patients who achieved CR or CRI as the time elapsed between date of CR/CRI and date of disease relapse or death from any cause
- 4) Percentage of patients who need transfusions (red blood cells and/or platelets), number of transfusions by patient
- 5) Patient quality of life evaluated using the EORTC QLQ-C30 version 3 scale
- 6) Number of hospitalizations (except scheduled protocol visit) required during the study

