5.6.2. Secondary Endpoint Definitions and Analyses

Secondary endpoints will be assessed on both the ITT and PP populations.

5.6.2.1. Complete Remission (CR), Complete Remission with Incomplete Recovery (neutrophil or platelet recovery, CRi, CRp), Partial Remission (PR)

Definitions for CR, CRi, and PR can be found in Table 4 below. This information will be collected in the section “AML-disease evaluation.” Responses are entered by the site in accordance with various criteria. Exploratory analyses may include imputed responses (not site defined) based on the data available per the criteria in Table 4 for the derivation of response.

Table 4: Definitions of CR, CRi, PR, Relapse

Category	Definition according to protocol V4 to V6	Definition according to protocol V7
Morphologic leukemia-free state	Bone marrow blasts < 5% No extramedullary disease	
Complete remission (CR)	Morphologic CR Bone marrow blasts < 5%; absence of blasts with Auer rods; absence of extramedullary disease; absolute neutrophil count $> 1.0 \times 10^9/L$ (1000/ μ L); platelet count $> 100 \times 10^9/L$ (100 000/ μ L); patient independent of transfusions Cytogenetic CR Cytogenetic normal (in those with previously abnormal cytogenetics) Molecular CR Molecular studies negative	
CR with incomplete recovery (CRi)	All CR criteria except for residual neutropenia ($< 1.0 \times 10^9/L$ [1000/ μ L]) OR thrombocytopenia ($< 100 \times 10^9/L$ [100 000/ μ L]). patient independent of transfusions	
Partial remission (PR)	All hematologic criteria of CR; decrease of bone marrow blast percentage to 5% to 25% And normalization of blood counts	
Relapse following CR	Bone marrow blasts $\geq 5%$; OR reappearance of blasts in the blood OR Development of extramedullary disease	

Percentages of patients with CR, CR or Cri, and PR will be calculated and presented by treatment group. All other subjects will be considered non-responders for determining the denominator. This objective response rate data (i.e. CR, CRi or PR) will be analyzed based on a logistic regression model with both treatment and PS included in the model. The treatment effect will be summarized with an adjusted Odds Ratio (OR) and 95% confidence interval. Percentage of patients with objective response will be calculated and associated exact 95% CIs will be presented by treatment group.

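### SAP 5.6.2.2 dates progression against baseline with no marrow or blood relapse trigger; this contradicts SAP 3.5.1 and protocol version 7, and SAP section 6 does not declare it

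*SAP*

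**What the plan says.** **The protocol rule.** Protocol 15.3.3 states: "PFS will be defined as the time from date of randomization and resistant disease or relapse or death from any cause". Protocol 4.3.2 says the same. Its Table 3 defines resistant disease as "BM blasts increase of at least 5% vs nadir AND/OR PBBC increase of at least 15% in absolute count vs nadir", or a rise of at least 50% in the blood percentage from nadir, with the qualifier "repeated at min 7 days interval". Relapse in Table 3 is marrow blasts of 5% or more, or "reappearance of blasts in the blood; or development of extramedullary disease".

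**The SAP, first place.** Section 3.5.1 repeats the protocol rule: "Progression-free survival (PFS) defined as the time elapsed between randomization and resistant disease or relapse or death from any cause".

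**The SAP, second place.** Section 5.6.2.2 makes the event progression or death from any cause. Progression is any one of three things: "At least a 25% increase of BMBC compared with baseline"; "At least a 50% increase of PBBC compared with baseline"; or extramedullary disease being present. The section points to an e-CRF page and says that potential events will be reviewed before lock.

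**Relapse elsewhere in the SAP.** The relapse row of Table 4 uses the 5% marrow threshold, "OR reappearance of blasts in the blood OR Development of extramedullary disease". Relapse-free survival (5.6.2.3) rests on relapse or death. Section 5.6.2.2 does not refer to Table 4.

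**Declared changes.** For the definition of PFS, SAP section 6 reports only that death now counts whatever its cause. Protocol version 7, on which the SAP says it is based, already contained that.

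**The concern.** The two rules differ in reference point (nadir or baseline), in confirmation (a repeat or none), and in whether a marrow or blood relapse after remission counts. The PFS date of a given patient therefore depends on which SAP section is programmed. A patient can have a relapse-free survival event and no PFS event, although PFS in SAP 3.5.1 includes relapse.

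PFS is a secondary endpoint. However, the SAP's Introduction says that activity will be judged on effects across several endpoints together. PFS also has its own log-rank, Cox and subgroup analyses. Under SAP 5.6.2.4 and 5.6.2.6 the same progression date ends the counting of transfusions and hospitalizations.

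**Working it through.** The plan gives no figure on this point to reproduce. The check applies both rules to the same blast values. The patients below are assumed, for illustration.

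**Formulas.** Let B be the baseline and N the nadir marrow blast percentage. The documents do not say whether 25% or 5% is relative or in percentage points, so both readings are shown.
- SAP 5.6.2.2 marrow threshold: 1.25 × B (relative) or B + 25 (points).
- Protocol Table 3 resistant disease, marrow: N + 5 (points) or 1.05 × N (relative).
- Relapse, marrow: 5%.

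**1. Level needed for a SAP event**

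| Baseline | Relative | Points | Relative level ÷ 5% |
|---|---|---|---|
| 15% | 18.75% | 40% | 3.75 |
| 20% | 25% | 45% | 5 |
| 30% | 37.5% | 55% | 7.5 |
| 40% | 50% | 65% | 10 |
| 60% | 75% | 85% | 15 |

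**2. Ceiling.** 1.25 × B exceeds 100 when B > 80, and B + 25 exceeds 100 when B > 75. Above those baselines the marrow criterion cannot be met.

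**3. Where the relapse gap starts.** 1.25 × B = 5 gives B = 4. On the relative reading the SAP threshold is above the relapse threshold for every baseline over 4%. On the points reading it is above it for every baseline.

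**4. Relapse after remission: 60% → 3% (CR) → 40%.** 40 is above 5, so this is relapse. It also lies outside the 5-10% band in which Table 3's footnote asks for a repeat marrow. 40 is below both 75 and 85, so there is no PFS event unless the blood or extramedullary criterion is met.

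**5. No remission: 60% → 30% → 45%, repeated after 7 days.** Table 3 needs 30 + 5 = 35, or 1.05 × 30 = 31.5, and both are met. The SAP needs 75 or 85, and neither is met. The gap is not confined to responders.

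**6. The other direction: baseline 15%, no fall, so N = 15 if nadir includes baseline.** The SAP relative threshold is 18.75% and the Table 3 points threshold is 15 + 5 = 20%. A value of 19% is a SAP event and not resistant disease. The crossover is 1.25 × B = B + 5, so B = 20. Below 20% the SAP can fire first on this pair of readings. It does not if the SAP is read in points (40%) or Table 3 as relative (15.75%). SAP 5.2.6 plans a subgroup with baseline blasts below 20%.

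**7. Two further routes to an earlier SAP date.** A single transient rise counts in 5.6.2.2, which asks for no repeat. Extramedullary disease already present at baseline also counts, because the criterion is presence and has no reference point.

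**8. Blood blasts.** No levels are computed because the unit is not fixed. SAP 5.8.2.1 lists blasts in percent under haematology but does not tie that to the progression criterion. A 50% rise from a zero baseline is undefined. The protocol's percentage limb has the same problem with a zero nadir, so this does not favour either rule.

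**9. Size of the exposed group.** Protocol 3.1 cites an 18% complete remission rate with low-dose cytarabine. Applied to all 123 patients as an assumption, 0.18 × 123 ≈ 22. At assumed rates of 10% and 30% the figures are about 12 and 37. These are responders whose relapse could be missed on marrow or blood, not a count of misdated patients.

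**The case against.** **Sources not visible.** Section 5.6.2.2 takes progression from an e-CRF page that is not available here, and potential events are reviewed before lock. Either might bring relapse or nadir in. This is fair as a caveat, but the SAP states no review criteria and the criteria it does print contain neither. The two columns of SAP Table 4 (protocol V4 to V6, and V7) are merged in the text, so the version to which its relapse row belongs cannot be read. The comparison does not depend on it, because protocol Table 3 gives the same three limbs.

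**A carry-over.** Protocol Appendix 11 says that version 7 re-defined the response criteria, so 5.6.2.2 may be older wording. The documents do not confirm this. It would explain the conflict without settling which rule governs.

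**Partial overlap.** The extramedullary criterion catches some relapses. This stands: the missing triggers are marrow and blood relapse, not every form of relapse.

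**Stronger readings that a reader might infer.** One is that the SAP rule always dates progression late. Steps 6 and 7 show that it can also be early. Another is that late counting of relapse favours the arm with more remissions. The documents do not support that either: non-responders are affected too, events can move both ways, and nothing gives the balance between arms. A third is that relapsed patients will go unobserved until death. Protocol 8.10 limits follow-up disease evaluation to patients without prior relapse, but Table 6 lists it without that condition and 8.11 allows continued treatment with the same visits. That consequence is possible, not established.

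**Conclusion.** The conflict is real and should be fixed before database lock. Both rules are current text, and they give different event dates for the same patient. On the marrow criterion the SAP rule misses relapses that protocol Table 3 and SAP Table 4 both define. The shortfall is large: at a 60% baseline it needs 15 times the relapse level on the relative reading, and above 80% (relative) or 75% (points) it cannot be met.

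The examples assume that no blood or extramedullary criterion is met. The early-dating example also assumes that nadir includes baseline, that the SAP's 25% is relative and that Table 3's 5% is in points.

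The net direction and size of the effect on the PFS hazard ratio cannot be determined from the documents. A reader might take this as a threat to the trial's main conclusion. It is not: the OS hazard-ratio decision does not use the progression date. What is affected is PFS as supporting evidence, and the descriptive transfusion and hospitalization counts. Confidence is high for the conflict and its non-declaration, and lower for how many patients it touches.

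**What to change.** Use one PFS event rule in SAP 3.5.1 and 5.6.2.2, matching protocol version 7: resistant disease as in Table 3 (from nadir, with the repeat), relapse after CR or CRi, or death. Count extramedullary disease when it is new or reappears after documented absence, not when it has merely persisted since baseline. A rule restricted to disease new since baseline would miss a patient who cleared it, reached remission and relapsed with it.

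State in the SAP:
- whether 5% from nadir is absolute or relative;
- the unit of the peripheral blood blast count;
- how a zero nadir is handled;
- how patients assessed under protocol versions 4 to 6 are derived when no repeat test exists.

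Carry out the pre-lock review of progression against this rule without knowledge of arm. Use the same date for the transfusion and hospitalization cut-offs. List any remaining departure from the protocol in SAP section 6. Keeping the baseline-referenced rule as a sensitivity analysis is optional.

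The cost is SAP wording and the programming of nadir, confirmation and relapse dates. PFS dates may move earlier or later, in responders and non-responders alike, and some events in patients assessed under versions 4 to 6 will remain unconfirmed.

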5.6.2.3. Relapse Free Survival (RFS)

Relapse free survival is defined for patients who have achieved CR or CRi, as time elapsed between date of CR or CRi and date of disease relapse or death from any cause. Patients not known to have any of these events will be censored on the date they were last known to be event-free.

Specifically, RFS will be analyzed at the time of final analysis using a stratified log-rank test (stratified by PS) and displayed using Kaplan-Meier curves. Furthermore, a Cox model will also be used to assess the effect of treatment and will include terms for prognostic factors (PS, age and karyotypic group). P-values for these analyses however will not be quoted as these are not randomised comparisons.

5.6.2.4. Transfusions

For collection of information regarding transfusions, the following variables will be collected at each visit:

- Transfusions (Yes/No)
If yes,
 - mean number of transfusions
 - mean weekly number of transfusions
 - mean number of units transfused
 - at least 1 transfusion of RBC (Yes/No)

- at least 1 transfusion of platelets (Yes/No)
- at least 1 transfusion of other (Yes/No) and specifications

Any transfusion occurring after a PD will not be taken into account.

The number of transfusions will be grouped by quarter, up to an event (PD/death) and overall, by treatment group, using descriptive statistics. The mean number of transfusions of RBC and/or platelets required during the study, along with a corresponding 95% CI, will be calculated.

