2. OBJECTIVES OF STATISTICAL ANALYSIS

This statistical analysis plan (SAP) is designed to outline the methods to be used in the analysis of study data in order to answer the study objective(s). Populations for analysis, data handling rules, statistical methods, and formats for data presentation are provided. The statistical analyses and summary tabulations described in this SAP will provide the basis for the results sections of the clinical study report (CSR) for this trial.

This SAP also will outline any differences in the currently planned analytical objectives relative to those planned in the study protocol.

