5. STATISTICAL METHODS

5.1. Sample Size Justification

The sample size calculation is based on the original primary efficacy endpoint (PFS). We assumed 75% improvement in median PFS in the GRASPA plus LDAC group (treatment) compared to median PFS in the LDAC group (control). This corresponded to a median PFS of 2 months for the null hypothesis and a median of 3.5 months for the alternative hypothesis. An assumption of 24 months of accrual time and whole study duration of 48 months was used. No dropout rate was taken into consideration.

With a two-sided 5% level significance test and a power of 80%, taking into account the unbalanced group size (1 : 2), a total of 117 patients should be enrolled in order to observe 117 PFS events.

The study was designed based on the initial primary endpoint using group sequential methodology, allowing for interim analysis for futility. In order to account for this, the sample size was increased from 117 to 123 patients (41 in the LDAC group and 82 in the GRASPA plus LDAC group).

However, the sponsor amended the study, and the primary endpoint was changed from PFS to OS. It is acknowledged that the study is not powered to detect a statistically significant difference in OS; rather this is a proof of concept signal seeking study. In light of this, the one-sided significance level will be 0.025.

A decision as to whether GRASPA appears to be a promising drug in this indication will be based on the numerical values for the hazard ratio for OS. A hazard ratio of ≤ 0.80 will indicate a 20% numerical reduction in the death rate on average over time in the GRASPA group compared to control.

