5.6.2.6. Hospitalizations

For collection of information regarding hospitalizations, the following variables will be collected at each visit:

- Hospitalization (Yes/No)
If yes,
 - mean number of hospitalizations
 - mean weekly number of hospitalizations
 - reasons for hospitalization
 - mean duration of hospitalization (days)

The duration of hospitalization will be defined in days as the following:

- If hospitalization lasts more than 24 hours, the duration=End Date - Beginning Date + 1
- If hospitalization lasts less than 24 hours, the duration=1 day

Any hospitalization occurring after a PD will not be taken into account.

The number of hospitalizations will be grouped by quarter, up to an event (PD/death) and overall, by treatment group, using descriptive statistics. The mean number of hospitalizations occurring during the study, along with a corresponding 95% CI, will be calculated.

Additionally, a special focus will be taken on hospitalization lasting more than 24 hours, and all previous variables will be described for hospitalizations lasting more than 24 hours.

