6. CHANGES TO PLANNED ANALYSES

Initially, this study was designed with Progression Free Survival as its primary endpoint. However, the protocol definition of PFS only considered death due to progression. It was recognised that this was not in line with regulatory guidance where death from any cause is included in the endpoint and the definition of PFS was therefore modified. Based on recommendations from the AML Advisory Board (meeting conducted on 24th January 2017) the primary endpoint was changed from PFS to overall survival.

A planned interim analysis for futility was not conducted.

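### Transfusion and hospitalisation counts lack a time denominator and a consistent counting window, and the SAP does not carry over the protocol's between-arm analysis of QoL deterioration

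*SAP*

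**What the plan says.** **Counts.** SAP 5.6.2.4: "Any transfusion occurring after a PD will not be taken into account". SAP 5.6.2.6: "Any hospitalization occurring after a PD will not be taken into account". In the same sections, counts are to be described by quarter, up to the PD or death event, and overall. The statistics that carry an interval are "The mean number of transfusions of RBC and/or platelets required during the study, along with a corresponding 95% CI, will be calculated" and "The mean number of hospitalizations occurring during the study, along with a corresponding 95% CI, will be calculated". A mean weekly number is listed for both endpoints, without a stated denominator or CI.

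Protocol 15.3.3 covers the percentage of patients transfused, the mean number of transfusions and the mean number of hospitalisations "required during the study will be described with their corresponding 95% CI in each treatment group". It does not stop counting at progression.

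**Declared changes.** SAP section 2 states: "This SAP also will outline any differences in the currently planned analytical objectives relative to those planned in the study protocol". SAP section 6 reports the PFS definition, the switch from PFS to OS, and "A planned interim analysis for futility was not conducted". The PD cut-off is not there.

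**Quality of life.** Protocol 15.3.3 plans Kaplan-Meier curves and a PS-stratified log-rank test between arms for time to QoL deterioration. SAP 5.6.2.5 defines the deterioration event and a 10% threshold but names no test, and its mixed model is run within each arm. Its threshold refers to a total QoL score, which is not among the scores the section lists. The output list in SAP 8.1 holds one QLQ-C30 table (14.2.10), and the time-to-event listing in SAP 8.2 (16.2.6.3) covers PFS and OS only.

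**The concern.** A mean count per patient is an event rate multiplied by time observed. If counting stops at PD or death, time observed is PFS time; if it runs to death, it is survival time. Either way, an arm that does better on the time-to-event endpoint accumulates more transfusions and admissions at the same underlying rate. The crude mean would then read as a burden of treatment when it partly reflects benefit.

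The decision criterion is the OS hazard ratio, and these endpoints are supportive. However, SAP section 1 says activity will be judged collectively across a range of endpoints, so a summary that penalises the arm with longer PFS or OS can distort that judgement. For QoL, the SAP as written specifies no between-arm comparison, although the protocol does. An unclear counting window also lets two programmers produce different tables from the same text.

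**Working it through.** **Inputs from the documents.** PFS medians: "This corresponded to a median PFS of 2 months for the null hypothesis and a median of 3.5 months for the alternative hypothesis" (SAP 5.1). OS medians 6.4 vs 8.0 months (SAP section 1). Follow-up is 24 months per patient, with the primary analysis once all patients have completed 12 months (protocol synopsis). Allocation is 41 control, 82 GRASPA.

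**Assumptions, not in the documents.** Exponential PFS and OS; the same event-rate function in both arms; a more modest PFS scenario of 2 vs 2.5 months (hazard ratio 0.80); and, for falling rates, a rate of 1 to month 2 and f thereafter. The documents give no event rates, but with equal rates the ratio of means does not depend on their level.

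**Check of the plan's own figure.** HR = 2/3.5 = 0.5714 and ln(1.75) = 0.5596. Schoenfeld events = (1.960 + 0.842)² / (1/3 × 2/3 × 0.5596²) = 113, or 114 in whole 1:2 blocks, against the stated 117 (power at 117 events: 81.4%). The medians are therefore read as the plan used them.

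**Crude mean at a constant rate.** Mean time at risk to cap T is (1 − exp(−λT))/λ, with λ = ln 2/median.

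| Scenario | Control, 24 mo | GRASPA, 24 mo | Ratio, 24 mo | Ratio, 12 mo |
|---|---|---|---|---|
| Count to PD/death, PFS 2 vs 3.5 | 2.885 | 5.006 | 1.74 | 1.61 |
| Count to PD/death, PFS 2 vs 2.5 | 2.885 | 3.602 | 1.25 | 1.22 |
| Count to death, OS 6.4 vs 8.0 | 8.547 | 10.099 | 1.18 | 1.11 |

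In the first row GRASPA would need a rate 1 − 2.885/5.006 = 42% lower for the crude means to be equal.

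**What the cut-off itself contributes.** Rows 2 and 3 share a hazard ratio of 0.80. Without a cap both ratios would be 1/0.80 = 1.25; they differ only because the 24-month cap trims OS time more. So the PD cut-off moves the ratio from 1.18 to 1.25. The rest of the 1.74 comes from the larger PFS effect assumed in row 1.

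**Falling rates, 2 vs 3.5 months, 24-month cap.** A falling rate is plausible, because CR in protocol Table 3 requires independence from red-cell transfusion. Expected counts are:
- f = 0.5: 2.164 vs 3.329, ratio 1.54
- f = 0.25: 1.803 vs 2.490, ratio 1.38

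The direction holds; the size shrinks.

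**Does a simple rate solve it?** Only if rates are constant. Dividing the counts above by time at risk:
- f = 0.5: (3.329/5.006)/(2.164/2.885) = 0.665/0.750 = 0.89
- f = 0.25: (2.490/5.006)/(1.803/2.885) = 0.497/0.625 = 0.80

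A single overall rate would therefore favour GRASPA, because its longer follow-up adds low-rate time. Stratifying by 3-month quarter (Mantel-Haenszel, 41 vs 82) brings the ratio to 0.982 and 0.967.

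**Sparseness.** With a 2-month control median, 41 × 0.5^(9/2) = 1.8 controls remain at risk at month 9 and 41 × 0.5^6 = 0.6 at month 12. Late quarters cannot stand alone. Under these scenarios the rate is constant after month 2, so pooling the later quarters introduces no distortion.

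**The case against.** **The cut-off may be a permitted convention.** Protocol 15.3 lets the SAP set further conventions, SAP section 1 says it adds analysis detail, and the promise in section 2 concerns analytical objectives, which have not changed. This has force: the omission is a gap in the change list, not clear proof of a breach. But a rule that decides which events count alters a planned analysis, and section 6 is where a reader would look for it.

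**The crude mean comes from the protocol.** This stands. A reader might infer that the PD cut-off creates the 1.74. The documents do not support that: the protocol's own mean has no denominator either, and at a hazard ratio of 0.80 the cut-off changes 1.18 to 1.25.

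**Time-adjusted summaries exist.** The weekly number and the quarterly grouping are in the SAP, and the yes/no transfusion variables are kept. What is missing is the denominator, an interval, and the protocol's CI for the percentage transfused.

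**The bias works against GRASPA.** This is correct. It cannot manufacture an efficacy signal, and the SAP names no between-arm test for counts, so no claim about significance follows.

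**The QoL test is still in the protocol.** SAP 5.2.1 has a general Kaplan-Meier statement and a two-sided 0.05 level for secondary efficacy endpoints, and output shells sit in a separate document. A reader might infer that the sponsor deliberately dropped the test; the documents show only an incomplete restatement. Even so, a generic sentence does not supply a stratified between-arm log-rank test.

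**Post-PD data may be missing.** A reader might infer from protocol 8.11 that every patient with PD moves to survival follow-up only. That sentence sits under the GRASPA-toxicity bullet. The relapse/resistant-disease bullet allows treatment and the same visits to continue.

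**Conclusion.** The point holds as a specification gap in supportive endpoints that should be closed. It has three parts.

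1. The counting window is internally inconsistent. A flat exclusion after PD stands beside overall counts and whole-study means, differs from protocol 15.3.3, and is absent from section 6. The text does not settle that the cut-off applies to every summary.
2. The only count statistic with an interval scales with time at risk. The direction needs only a longer PFS (with the cut-off) or a longer OS (without it) on GRASPA. The size is illustrative: 1.18 to 1.74 over 24 months at equal constant rates, and 1.38 to 1.54 with falling rates at 2 vs 3.5 months. It rests on exponential times, equal rate functions, and, for the upper end, the original PFS sizing assumption.
3. The SAP does not carry over the protocol's between-arm analysis of time to QoL deterioration, and the score to which the threshold applies is not identified.

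None of this touches the OS hazard ratio criterion.

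**What to change.** 1. **Counting window.** Reconcile the wording in SAP 5.6.2.4 and 5.6.2.6, and list any PD cut-off in section 6.
2. **Rate.** Beside the crude mean, report events per patient-time at risk, including patients with no events, with a CI in each arm. Define the mean weekly number this way. Show it by quarter with patient-time denominators and late quarters pooled. Label it a descriptive pre-PD rate. A between-arm rate ratio is optional and exploratory, since the protocol plans only per-arm description.
3. **Protocol summaries.** Report the whole-study count and rate as far as post-PD data were collected, and the percentage transfused with its CI.
4. **QoL.** Restore the Kaplan-Meier and PS-stratified log-rank analysis of time to deterioration in SAP 5.6.2.5 and the output list, on one named score, keeping the 10% threshold. The listed global QoL scale is the likely intent, for the sponsor to confirm.

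**Cost.** SAP wording and a few outputs, before database lock. Items 1, 2 and 4 use data already planned. Item 3 depends on post-PD capture, which is uncertain: protocol 8.8 and 8.10 provide for it, but protocol Table 6 and SAP Table 3 do not list transfusions or hospitalisations at follow-up. Collection should be checked before item 3 is promised.
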